### **3.4 Replacement of Subjects**

Subjects who are withdrawn from the study may be replaced at the discretion of the investigator in consultation with Amgen.

### **3.5 Estimated Study Duration**

#### **3.5.1 Study Duration for Subjects**

The estimated study duration is 6 weeks, which includes up to a 14 day screening period and 30 days on study.

#### **3.5.2 End of Study**

Primary Completion: the time when the last subject is assessed or receives an intervention for the purposes of final collection of data for the primary analysis. Subjects with clinically significant adverse events at the end of study will be followed until resolution of the adverse event or until it is considered clinically stable.

## **4. SUBJECT ELIGIBILITY**

Investigators will be expected to maintain a screening log of all potential study candidates that includes limited information about the potential candidate (eg, date of screening).

Before any study-specific activities/procedure, the appropriate written informed consent must be obtained from the subject's legally acceptable representative (LAR) (see [Section 11.1](#)).

In addition to written informed consent from a legally acceptable representative, the assent of the child must also be obtained as appropriate to the age of the subject and/or based on local regulations.

### **4.1 Inclusion Criteria**

- 101 Subject's legally acceptable representative has provided informed consent and the subject has provided written assent based on local regulations and/or guidelines prior to any study-specific activities/procedures being initiated.
- 102 Male or female subjects (aged 2 to less than 18 years) diagnosed with CKD and sHPT and receiving maintenance haemodialysis or haemodiafiltration for > 30 days prior to screening.
- 103 Subject must be on a dialysate calcium concentration of  $\geq 2.5$  mEq/L (1.25 mmol/L) for at least 1 month prior to enrollment and throughout the duration of the study.
- 104 Screening and Baseline serum PTH level  $> 200$  pg/mL (21 pmol/L).
- 105 Subject must weigh  $\geq 7$  kg at Baseline (Day -2).
- 106 Screening and Baseline serum corrected calcium from the local laboratory  $\geq 9$  mg/dL (2.25 mmol/L).

- 107 Subjects on anti-convulsant medication must be on a stable dose for 3 months.
- 108 Free of any disease or condition other than those diseases or conditions related to their renal disease that, in the opinion of the investigator, would impact the subject's safety or the integrity of the study data.

#### 4.2 Exclusion Criteria

- 201 Currently receiving or has received any investigational drug (or is currently using an investigational device) within the 30 days or 5 half-lives (whichever is longer), prior to receiving the first dose of etelcalcetide. Other investigational procedures while participating in this study are excluded.
- 202 Subject previously has entered this study or previously exposed to etelcalcetide.
- 203 All herbal medicines (eg, St. John's wort), vitamins, and supplements consumed by the subject within the 30 days prior to receiving the first dose of etelcalcetide, and continuing use if applicable, will be reviewed by the Principal Investigator and the Amgen Medical Monitor. Written documentation of this review and Amgen acknowledgment is required for subject participation.
- 204 Use of any over-the-counter or prescription medications within the 14 days or 5 half-lives (whichever is longer) prior to receiving the first dose of etelcalcetide that are not established therapies for subjects with renal disease or other conditions secondary to renal disease will be reviewed by the Principal Investigator and the Amgen Medical Monitor. Written documentation of this review and Amgen acknowledgment is required for subject participation. Paracetamol (up to 2 g per day) for analgesia will be allowed.
- 205 Malignancy except non-melanoma skin cancers, within the last 5 years.
- 206 History of hypersensitivity or allergic reaction to any of the excipients listed in [Section 6.2.1](#).
- 207 Subject received cinacalcet therapy within less than 30 days prior to etelcalcetide dosing.
- 208 A new onset of seizure or worsening of a pre-existing seizure disorder within 2 months prior to etelcalcetide administration.
- 209 Subject's screening 12-lead ECG suggests unstable arrhythmia or other cardiac abnormality that could place the subject at increased risk, based upon the Investigator's opinion.
- 210 History of prolongation of the QT interval (eg, congenital long QT interval, second or third degree heart block or other conditions which prolong the QT interval) or history of ventricular arrhythmias.
- 211 Concurrent or within 28 days prior to enrollment use of medications that prolong QT interval (eg, sotalol, amiodarone, erythromycin, or clarithromycin). Please refer to the complete QT prolongation medication list at <http://www.crediblemeds.org/pdftemp/pdf/CompositeList.pdf>
- 212 Subjects with a corrected QT Interval (QTc) > 500 ms during screening, using Bazett's formula.
- 213 Subject has a history of symptomatic ventricular dysrhythmias or Torsades de Pointes.

214 Subject has a screening ALT or AST from the local lab  $\geq$  1.5 times the upper limit of normal (ULN).

215 Female subjects of childbearing potential who are unwilling to practice true sexual abstinence or use an acceptable method(s) of effective birth control during treatment through 3 months after receiving the etelcalcetide. Female subjects are considered of childbearing potential following menarche. Female subjects who have reached puberty must receive pregnancy prevention (sexual) counseling and be advised of the risk to the fetus if they become pregnant during treatment and for an additional 3 months after receiving the study drug. Acceptable methods of effective birth control include True sexual abstinence (The reliability of sexual abstinence must be evaluated by the investigator and be the preferred and usual lifestyle of the subject.); Hormonal (Combined estrogen and progestogen or progesterone-only hormonal contraception given via oral, intravaginal, transdermal, injectable, or implantable route); Intrauterine device (IUD); Intrauterine hormonal-releasing system (IUS); Two barrier methods (one by each partner) and the female partner must use spermicide with the barrier method [the male must use a condom (latex or other synthetic material) and the female may select either a diaphragm, cervical cap or contraceptive sponge. A female condom is not an option because there is a risk of tearing when both partners use a condom. The two-barrier is acceptable in countries where spermicide is not available.

216 Post-menarchal subject who is pregnant or breastfeeding, or is planning to become pregnant or breastfeed during treatment and for an additional 3 months after etelcalcetide administration. Female subjects with a positive pregnancy test at screening.

217 Subject likely to not be available to complete all protocol-required study visits or procedures, and/or to comply with all required study procedures to the best of the subject and investigator's knowledge.

## 5. SUBJECT ENROLLMENT

Before subjects begin participation in any study-specific activities/procedures, Amgen requires a copy of the site's written institutional review board/independent ethics committee (IRB/IEC) approval of the protocol, informed consent form, and all other subject information and/or recruitment material, if applicable (see [Section 11.2](#)). The subject's legally acceptable representatives (LAR) must personally sign and date the informed consent form before commencement of study-specific activities/procedures.

Adverse Events are to be collected for a subject once they have received the dose of investigational product (IP). A subject is considered enrolled once they have met all eligibility criteria based on screening and Day -2 (Baseline Visit) assessments.

Provided all eligibility criteria have been met, subjects will be asked to return to the research facility for admission on Day -2 (Baseline Visit) where additional assessments will be performed to confirm that the subject remains eligible for the study. If subject

eligibility is confirmed, the subject will be assigned to Cohort 1 or Cohort 2 based on the subject's age at screening:

- Cohort 1 → At least 5 subjects age 12 to < 18 years
- Cohort 2 → At least 5 subjects age 2 to < 12 years

Cumulative data from 2 subjects enrolled in Cohort 1 will be reviewed prior to enrolling subjects in Cohort 2 (see [section 6.2.1](#)).

The investigator is to document the enrollment decision and date, in the subject's medical record and in/on the enrollment CRF.

Each subject who enters into the screening period for the study (defined as when the LAR signs the informed consent) receives a unique subject identification number before any study procedures are performed. The subject identification number will be assigned manually. This number will be used to identify the subject throughout the clinical study and must be used on all study documentation related to that subject. Subjects may be rescreened at the discretion of the investigator in consultation with the Amgen Medical Monitor.

The subject identification number must remain constant throughout the entire clinical study; it must not be changed after initial assignment, including if a subject is rescreened.

## **6. TREATMENT PROCEDURES**

### **6.1 Classification of Product(s) and/or Medical Device(s)**

The Amgen Investigational Product(s) used in this study include: Etelcalcetide.

The Investigational Product Instruction Manual (IPIM), a document external to this protocol, contains detailed information regarding the storage, preparation, destruction, and administration of etelcalcetide.

### **6.2 Investigational Product**

All investigational product(s) will be administered at the research facility by a qualified staff member.

A physician must be available at the time of administration of Investigational Product.

#### **6.2.1 Amgen Investigational Product Etelcalcetide (AMG 416)**

Etelcalcetide drug product will be manufactured and packaged by Amgen Inc. and distributed using Amgen clinical study drug distribution procedures. The active

pharmaceutical ingredient (API) is an eight-amino acid synthetic peptide prepared as a hydrochloride salt.

Etelcalcetide drug product will be presented as a sterile, preservative-free, aqueous solution containing 10 mg etelcalcetide free base, CC mg sodium chloride and CC mg succinic acid, in a single-use 3 mL glass vial. The drug product vial contains 2 mL of clear, colorless solution with etelcalcetide concentration of 5 mg/mL. The solution is ready to administer and has pH between CCI and CCI. The recommended storage condition for etelcalcetide liquid drug product is between C°C to C°C, protect from light.

#### **6.2.1.1 Dosage, Administration, and Schedule**

Prior to administration of study drug, a pharmacist, pharmacy technician, or other appropriately qualified staff member, other than the staff member who prepared the dose, will check the dosing preparation to ensure the correct investigational product has been used, the dose level is correct and the investigational product is within expiration date. An Amgen monitor may also be present to ensure study drug is prepared according to the protocol.

Etelcalcetide will be administered at the research facility by a qualified staff member, under the supervision of a licensed physician. The date, time, administered volume, concentration (as applicable) and lot number of the investigational product will be recorded in the subject records and on the individual subject's electronic case report form (CRF).

A single dose of etelcalcetide is to be administered by IV bolus administration at 0.035 mg/kg given into the venous line of the dialysis circuit at the end of haemodialysis session. Etelcalcetide will be administered during rinse back to ensure the investigational product reaches the systemic circulation.

Overdosage of etelcalcetide may lead to hypocalcemia with or without clinical symptoms and may require treatment (see Warnings and Precautions, [Etelcalcetide Investigator's Brochure](#)). No cases of overdose were reported in two pivotal double-blind placebo-controlled Phase 3 clinical trials.

While etelcalcetide is dialyzable, haemodialysis has not been studied as a treatment for overdosage.

#### **6.2.1.2 Safety Monitoring and Data Review**

The investigator will be responsible for routine monitoring of subject safety during the study and any follow-up period necessary for events requiring continued monitoring

---

beyond end of study. The Amgen Medical Monitor and Amgen Global Safety Officer (GSO) or designee will review each subject's cumulative safety data through end of study on an ongoing basis.

Additionally, after end of study visits have been completed for 2 subjects enrolled in Cohort 1, cumulative study data will be reviewed by a team composed of the Investigator(s), Amgen Medical Monitor, Amgen Global Safety Officer (GSO) or designee and additional members as needed (eg, Amgen Clinical Research Study Manager (CRSM), Biostatistician, PK Scientist, etc.). The voting members include the Principal Investigator or designee, Amgen Medical Monitor, and Amgen Global Safety Officer or designee. All available study data, including demographics, IP administration, medical history, concomitant medications, adverse events, ECGs, vital signs, laboratory and PK results will be reviewed. Data review will not require that all queries be resolved or source verified. Cohort 2 will open for enrollment when the dose has been found to be reasonably tolerated based on available study data for at least 2 subjects enrolled in Cohort 1 and upon unanimous decision by the review committee. Based on emerging safety and PK data, the review committee may make other decisions (eg., lower the dose level, enroll additional subjects in Cohort 1, etc.). All decisions will be documented in meeting minutes.

#### **6.2.2            Cohort Stopping Rules**

Dosing within the cohort will be stopped if suspected treatment-related AEs or changes in vital signs, ECGs or clinical laboratory results are observed and pose a significant health risk to the subject. In addition, dosing within the cohort will be stopped for any occurrence of the following:

- suspected treatment-related Common Terminology Criteria for Adverse Events (CTCAE) v4.0 Grade 2 adverse events in 2 or more subjects; or
- 2 separate, suspected treatment-related CTCAE v4.0 Grade 2 adverse events in a single subject;

or

- suspected treatment-related CTCAE v4.0 Grade 3 or greater adverse event in a single subject or
- suspected treatment-related serious adverse event (SAE) in a single subject

The review team will be convened, and the event and all relevant safety data will be reviewed for evidence of relationship to treatment and clinical or medical significance.

Dosing of additional subjects in the cohort may only be resumed upon unanimous vote by the Investigator(s), Amgen Medical Monitor, and Amgen GSO.

The review of safety data and dosing decisions will be documented in meeting minutes. Amgen will issue a written notification of the dosing decision to the Investigator(s).

### **6.3 Criteria for Additional Safety Assessment due to Potential Hepatotoxicity**

Subjects should be followed according to the recommendations in Appendix B (Additional Safety Assessment Information) for possible drug-induced liver injury (DILI), if ALL of the criteria below are met:

- Increased AST or ALT from the relevant baseline value as specified below:

Baseline AST or ALT value	AST or ALT elevation
< ULN	> 3x ULN

AND

- TBIL > 2x upper limit of normal (ULN) or INR > 1.5

AND

- No other cause for the combination of the above laboratory abnormalities is immediately apparent; important alternative causes for elevated AST/ALT and/or elevated TBIL values include, but are not limited to:
  - Hepatobiliary tract disease
  - Viral hepatitis (eg, Hepatitis A/B/C/D/E, Epstein-Barr Virus, Cytomegalovirus, Herpes Simplex Virus, Varicella, Toxoplasmosis, and Parvovirus)
  - Right sided heart failure, hypotension or any cause of hypoxia to the liver causing ischemia
  - Exposure to hepatotoxic agents/drugs including herbal and dietary supplements, plants, and mushrooms
  - Heritable disorders causing impaired glucuronidation (eg, Gilbert's syndrome, Crigler-Najjar syndrome) and drugs that inhibit bilirubin glucuronidation (eg, indinavir, atazanavir)
  - Alpha-one antitrypsin deficiency
  - Alcoholic hepatitis
  - Autoimmune hepatitis
  - Wilson's disease and hemochromatosis
  - Non-alcoholic Fatty Liver Disease including Steatohepatitis (NASH)
  - Non-hepatic causes (e.g. rhabdomyolysis, hemolysis)

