#### **9.1.2              Serious Adverse Events**

A serious adverse event is defined as an adverse event that meets at least 1 of the following serious criteria:

- fatal
- life threatening (places the subject at immediate risk of death)
- requires in patient hospitalization or prolongation of existing hospitalization
- results in persistent or significant disability/incapacity
- congenital anomaly/birth defect
- other medically important serious event

An adverse event would meet the criterion of “requires hospitalization”, if the event necessitated an admission to a health care facility (eg, overnight stay).

If an investigator considers an event to be clinically important, but it does not meet any of the serious criteria, the event could be classified as a serious adverse event under the criterion of “other medically important serious event”. Examples of such events could include allergic bronchospasm, convulsions, blood dyscrasias, drug induced liver injury (DILI) (see [Appendix A](#) for DILI reporting criteria), or events that necessitate an emergency room visit, outpatient surgery, or urgent intervention.

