### Drug-induced Liver Injury Reporting & Additional Assessments

#### Reporting

To facilitate appropriate monitoring for signals of DILI, cases of concurrent AST or ALT and TBL and/or INR elevation according to the criteria specified in [Section 6.3](#) require the following:

- The event is to be reported to Amgen as a serious adverse event within 24 hours of discovery or notification of the event (ie, before additional etiologic investigations have been concluded)
- The appropriate CRF (eg, Event CRF) that captures information necessary to facilitate the evaluation of treatment-emergent liver abnormalities is to be completed and sent to the Amgen.

Other events of hepatotoxicity and potential DILI are to be reported as serious adverse events if they meet the criteria for a serious adverse event defined in [Section 9.2.2](#).

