#### Additional Clinical Assessments and Observation

All subjects in whom investigational product(s) or protocol-required therapies is/are withheld (either permanently or conditionally) due to potential DILI as specified in [Section 6.3](#) or who experience AST or ALT elevations  $> 3 \times$  ULN are to undergo a period of “close observation” until abnormalities return to normal or to the subject’s baseline levels. Assessments that are to be performed during this period include:

- Repeat AST, ALT, ALP, bilirubin (total and direct), and INR within 24 hours
- In cases of TBL  $> 2 \times$  ULN or INR  $> 1.5$ , retesting of liver tests, BIL (total and direct), and INR is to be performed every 24 hours until laboratory abnormalities improve
- Testing frequency of the above laboratory tests may decrease if the abnormalities stabilize or the investigational product(s) or protocol-required therapies has/have been discontinued AND the subject is asymptomatic.
- Initiate investigation of alternative causes for elevated AST or ALT and/or elevated TBL:
  - Obtain complete blood count (CBC) with differential to assess for eosinophilia
  - Obtain serum total immunoglobulin IgG, Anti-nuclear antibody (ANA), Anti Smooth Muscle Antibody, and Liver Kidney Microsomal antibody 1 (LKM1) to assess for autoimmune hepatitis

- Obtain serum acetaminophen (paracetamol) levels
- Obtain a more detailed history of:
  - Prior and/or concurrent diseases or illness
  - Exposure to environmental and/or industrial chemical agents
  - Symptoms (if applicable) including right upper quadrant pain, hypersensitivity-type reactions, fatigue, nausea, vomiting and fever
  - Prior and/or concurrent use of alcohol, recreational drugs and special diets
  - Concomitant use of medications (including non-prescription medicines and herbal and dietary supplements), plants, and mushrooms
- Obtain viral serologies
- Obtain CPK, haptoglobin, LDH, and peripheral blood smear
- Perform appropriate liver imaging if clinically indicated
- Obtain appropriate blood sampling for pharmacokinetic analysis if this has not already been collected
- Obtain hepatology consult (liver biopsy may be considered in consultation with an hepatologist)

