**Treatment-Related AE:**

A treatment-related AE is any treatment-emergent AE that per investigator's review has a reasonable possibility of being caused by the investigational product.

Baseline

For any variable, unless otherwise defined, baseline is the last assessment taken prior to the first investigational product administration.

Baseline iPTH, cCa, total calcium, ionized calcium are defined as the average of screening and Day -2 assessments. If not all the values are available, the average will be calculated based on available value(s).

Baseline pre-dialysis ECG parameters including PR, QRS, QT, QTcB and QTcF are defined as the average of last non-missing pre-dialysis screening assessment and Study Day -2 pre-dialysis assessment.

---

The use of concomitant medication of interest at baseline is defined as use of each concomitant medication on Study Day 1. This includes medication use that starts prior to Study Day 1 and ends on Study Day 1 or duration of use covers Study Day 1.

Change from Baseline

The arithmetic difference between a post-baseline value and the baseline value:

Change (absolute) from Baseline = (Post-baseline Value – Baseline Value)

Percent change from Baseline

Percent Change from Baseline = [(Post-baseline Value – Baseline Value) / Baseline Value] x 100

Body Mass Index (BMI)

BMI will be calculated as weight (kg)/ [height (m)] in the clinical database.

Corrected (Bazett) QT Interval (QTcB)

The Bazett correction will be calculated from the investigator reported QT (msec) and RR interval (msec) (QTcB=QT/(RR/1000)0.50).

Corrected (Fridericia) QT Interval (QTcF)

The Fridericia correction will be calculated from the investigator reported QT (msec) and RR interval (msec) (QTcF=QT/(RR/1000)0.33).

End-of-Study

The EOS is the last planned clinical visit for each subject enrolled in this study. The last planned visit day for subjects in cohort 1 and 2 is on Study Day 30.

Subject-level End of Study (EOS) Date

End of study for each subject is defined as the date the subject last participated in the study. The date will be recorded on the End of Study CRF page.

Enrollment

A subject will be considered enrolled when the Investigator decides that the subject has met all eligibility criteria. Enrollment Date is defined as the date collected on the CRF.

Investigational Product

The term investigational product is used in reference to etelcalcetide.

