#### **10.5.2        Laboratory Test Results**

Hematology and chemistry data will be listed and reviewed for each subject. Values outside the normal laboratory reference range will be flagged as high or low on the listings. In addition, subject incidence of low corrected calcium (<7.0 mg/dL, <7.5 mg/dL, <8.0 mg/dL and <8.3 mg/dL) post-baseline will be provided. Summaries of key laboratory values [albumin corrected calcium (cCalcium), phosphorus, potassium, parathyroid hormone (PTH)] over time and changes from baseline over time will also be provided at each time point when samples are collected.

---

A summary of potential Hy's law cases meeting lab criteria will be provided. Subject incidence meeting the following criteria will be provided at baseline and post-baseline:

- 1) ALT or AST > 3 x ULN
- 2) Total bilirubin (TBL) > 2 x ULN
- 3) ALT or AST > 3 x ULN and TBL > 2 x ULN
- 4) ALT or AST > 3 x ULN and TBL > 2 x ULN and ALP < 2 x ULN

For post-baseline, if more than one value exist for a lab measure, the highest value will be used for these evaluations.

For subjects who meet the Hy's law lab criteria, information on their medical history and concomitant medication will be provided to further evaluate whether these are true Hy's law cases.

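### The DILI trigger in Protocol 6.3 has no AST/ALT threshold for enzymes at ULN to below 1.5 x ULN, which criterion 214 admits, so the automatic 24-hour report cannot fire through them

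*Protocol*

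**What the plan says.** - **Trigger.** Protocol 6.3 sets criteria that must all be met. The first is "Increased AST or ALT from the relevant baseline value as specified below". Its table has a single row, baseline below ULN with elevation above 3 x ULN. The others are total bilirubin above 2 x ULN or INR above 1.5, and no other immediately apparent cause.
- **Eligibility.** Criterion 214 in Protocol 4.2 excludes a child when "Subject has a screening ALT or AST from the local lab" is at or above 1.5 x ULN. Lower values are allowed.
- **Automatic report.** For cases meeting 6.3, Protocol Appendix A states: "The event is to be reported to Amgen as a serious adverse event within 24 hours of discovery or notification of the event". This applies before the cause has been worked up.
- **Everything else.** Appendix A continues: "Other events of hepatotoxicity and potential DILI are to be reported as serious adverse events if they meet the criteria" for an SAE. Protocol 9.1.2 says of an event that is clinically important but meets no serious criterion that "the event could be classified as a serious adverse event under the criterion of" other medical importance, and it lists DILI as an example.
- **Observation.** Appendix A requires close observation for subjects in whom product is withheld for potential DILI "or who experience AST or ALT elevations" above 3 x ULN, with no baseline condition.
- **Analysis.** SAP 10.5.2 plans a Hy's law summary: "Subject incidence meeting the following criteria will be provided at baseline and post-baseline". Its ALT/AST limit is also above 3 x ULN, with no baseline condition.

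**The concern.** The range of baselines the protocol admits is wider than the range for which 6.3 defines an enzyme threshold. For an enzyme that starts in the uncovered part, the first criterion has no value to compare against. Because all criteria must hold, 6.3 then cannot be met through that enzyme.

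What is lost is the automatic SAE classification with its 24-hour clock. Reporting then depends on the general serious criteria. Unless one of the concrete ones applies (hospitalization, for example), the DILI wording in 9.1.2 is permissive. It also sends the reader to Appendix A for the DILI reporting criteria, and Appendix A sends the reader back to 6.3.

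There is a second effect. A single suspected treatment-related SAE stops dosing in the cohort under Protocol 6.2.2, so that arm of the stopping rule also becomes a matter of judgement for these children. According to Protocol 2.3, etelcalcetide had not previously been studied in paediatric patients, so a mandatory safety report should reach every eligible child.

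**Working it through.** The plan states no figure for this point, so there is nothing to reproduce. The check compares two ranges and then follows the cross-references.

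**1. Ranges, per enzyme, in multiples of ULN**

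| Source | Range |
|---|---|
| Admitted by criterion 214 | below 1.5 |
| Given a threshold in 6.3 | below 1.0 |
| Admitted without a threshold | 1.0 to below 1.5 |

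A value exactly at ULN is in the gap.

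**2. Does the Day -2 visit close the gap?** No.
- Protocol Table 1 schedules clinical chemistry only at screening and Day 30. On Day -2 the blood tests are ionized and corrected calcium, albumin, PTH and the antibody sample.
- Table 3 agrees: there are 2 full safety panels (5.6 mL each above 12 kg). Section 7.2.14 gives the Day -2 safety/PD draw as 3.1 mL, which is the calcium, albumin and PTH volume. The synopsis mentions safety laboratory testing on Day -2, but the schedule and volumes do not include liver enzymes.
- Protocol 6.3 does not define its baseline. Under SAP section 6, "baseline is the last assessment taken prior to the first investigational product administration". For AST and ALT this is normally the same screening value that criterion 214 tests.

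**3. Following the references.** Appendix A ties the 24-hour report to 6.3. Outside 6.3 it relies on the general serious criteria, and the DILI example in 9.1.2 points back to Appendix A. No other text gives a threshold for a baseline at or above ULN.

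**4. How large a rise is above 3 x ULN?** Fold rise needed = 3 / baseline.
- Baseline 1.0: 3 / 1.0 = 3.0-fold
- Baseline 1.25: 3 / 1.25 = 2.4-fold
- Baseline approaching 1.5: 3 / 1.5 = 2.0-fold (the limit, so just over 2.0)

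Applying this limit throughout the gap would therefore still require more than a doubling, and the bilirubin/INR and no-other-cause criteria would remain.

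**5. How likely is a child in the gap?** The documents do not give the share p of children with an enzyme there, so p is assumed. With n = 10, the planned minimum, and children treated as independent, P(at least one) = 1 - (1 - p)^10.

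| Assumed p | Calculation | P(at least one of 10) |
|---|---|---|
| 5% | 1 - 0.95^10 | 0.401 |
| 10% | 1 - 0.90^10 | 0.651 |
| 20% | 1 - 0.80^10 | 0.893 |

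These are chances of enrolling a child with at least one enzyme in the gap. They are not chances of liver injury or of a missed report.

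**The case against.** **The table may have lost a row when the PDF was read.** A table indexed by baseline value looks built for more than one row. This cannot be fully excluded and should be checked against the source document. As it stands, the table reads as a complete header and row.

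**Clinical care is unaffected.** This stands. Close observation in Appendix A covers any AST or ALT above 3 x ULN, with repeat tests within 24 hours and a work-up of other causes. In a single-dose study there is also no later dose to withhold from that child.

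**Other routes to reporting remain.** Also true. Any SAE is reportable within 24 hours under Protocol 9.2.2. The Medical Monitor and Global Safety Officer review each subject's safety data on an ongoing basis (6.2.1.2), and the other stopping-rule arms in 6.2.2 still operate. A case would go unreported only if an investigator saw raised enzymes together with raised bilirubin or INR and no apparent cause, and judged the event not serious. That is unlikely, but an automatic rule exists so that the report does not depend on this judgement.

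**The probabilities overstate the gap.** Partly right. The criterion accepts AST or ALT, so a child with one enzyme below ULN can still qualify through it. The fully uncovered children are those with both enzymes in the gap, a group no larger than the one counted. The assumed shares have no basis in the documents.

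**The documents do not dictate the remedy.** A threshold above 3 x baseline is also possible. It would put the trigger between 3 x 1.0 = 3.0 and just under 3 x 1.5 = 4.5 x ULN, and so would differ from the limit in Appendix A and the SAP.

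These points limit the size of the problem. They do not remove the mismatch.

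**Conclusion.** The concern holds. On the text available, an enzyme starting at ULN to below 1.5 x ULN is eligible but cannot satisfy 6.3, so the automatic 24-hour SAE report is not triggered through it. A child could be under close observation and counted in the SAP's Hy's law table, yet fall outside the prompt reporting rule. No reason is given for limiting 6.3 to baselines below ULN.

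The expected effect is small: a qualifying event should be rare after a single dose, each child has only one scheduled post-dose AST/ALT (Day 30), and the other safeguards remain. The gap still merits correction because it concerns a mandatory safety report and the remedy costs almost nothing. Confidence is medium. The conclusion rests on the table being complete as read and on the screening value serving as baseline.

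**What to change.** In Protocol 6.3, make the AST/ALT criterion apply to every eligible baseline. Either remove the condition that baseline is below ULN, or add a row for baseline at or above ULN and below 1.5 x ULN with the same limit, above 3 x ULN. This is preferable to a multiple of baseline because it matches the limit already used in Appendix A and SAP 10.5.2. It would also help to state that the relevant baseline is the last pre-dose value, normally screening.

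As a clerical correction, 6.3 cites Appendix B for the additional safety assessment information. The appendix with that title is Appendix A; Appendix B is the sample SAE form.

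The cost is protocol wording only. No samples, visits or analyses are added.
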